### **7.3 Biohazard Containment**

As the transmission of HIV and other blood-borne pathogens can occur through contact with contaminated fluid, appropriate secretion precautions will be employed by all personnel in the handling of all specimens for this study as recommended by the CDC and NIH.

## **8 Assessment of Safety and Clinical Management**

### **8.1 Safety Monitoring**

The study site investigators are responsible for continuous close safety monitoring of all study participants and for alerting the Protocol Chairs if unexpected concerns arise. Appropriate safety monitoring will be contingent upon excellent communication between study participants and study staff, and upon cooperation among study staff, and the physician investigator.

Given this study involves a single study visit, use of placebo films which are immediately removed after insertion, and poses minimal risk to the participant, adverse events are not expected. In the very unlikely event that an unanticipated event occurs, the protocol chair and the DAIDS medical officers will be made aware of the event, and the event will be reported as applicable to the policies outlined on the IRB website: [www.irb.pitt.edu](http://www.irb.pitt.edu).

### **8.2 Adverse Events Definitions**

An AE is defined as any untoward medical occurrence in a clinical research participant administered an investigational product and which does not necessarily have a causal relationship with the investigational product. As such, an AE can be an unfavorable or unintended sign (including an abnormal laboratory finding, for example), symptom or disease temporally associated with the use of an investigational product, whether or not considered related to the product. The term “investigational product” for this study refers to the two placebo films.

Given that the study product is a placebo product and the product will be removed immediately after insertion, it is exceptionally unlikely that any adverse events will be noted during the single visit. Nonetheless, should one occur study site staff will document any AEs in source documents regardless of severity and presumed relationship to study product.

The PI/designee will grade the severity of each AE and the relationship of the AE to study product:

AE severity will be graded per the DAIDS Table for Grading Adult and Pediatric Adverse Events, Version 2.0, November 2014 and the Female Genital Grading Table for Use in Microbicide Studies (Appendix 1 to the DAIDS Table for Grading Adult and Pediatric Adverse Events, Version 2.0, December 2014). AEs not included in the Female Genital Grading Table will be graded by the DAIDS AE Grading Table Version 1.0, December 2004. In cases where a genital AE is covered in both tables, the Female Genital Grading Table for Use in Microbicide Studies will be the grading scale utilized.

The relationship of all AEs reported on CRFs will be assessed based on the Manual for Expedited Reporting of Adverse Events to DAIDS (Version 1.0, dated January 2010), the product Package Inserts and Investigators Brochures, and the clinical judgment of the PI/designee. Per the Manual for Expedited Reporting of Adverse Events to DAIDS, the relationship categories that will be used for this study are:

- *Related*: There is a reasonable possibility that the AE may be related to the study agent(s)
- *Not related*: There is not a reasonable possibility that the AE is related to the study agent(s)

The DAIDS Table for Grading Adult and Pediatric Adverse Events, the Female Genital Grading Table for Use in Microbicide Studies, and Version 2.0 of the Manual for Expedited Reporting of Adverse Events to DAIDS are available on the DAIDS Regulatory Support Center (RSC) web site: <http://rsc.tech-res.com/>

All AEs will be captured on an AE log form.

### **8.3 Criteria for Early Termination of Study Participation**

Participants may voluntarily withdraw from the study for any reason at any time. The Site PI/designee also may withdraw participants from the study to protect their safety and/or if they are unwilling or unable to comply with required study procedures.

## **9 Statistical Considerations**

### **9.1 Sample Size and Accrual**

The primary aim of the study is to assess proper placement of two vaginal placebo films containing two levels of polymer. Secondary aims are to gather women's preference and experiences through questionnaire and discussion.

In a previous cross-over study of placebo film products, the proportion of 32 women that misplaced a 2" x 2" cellulose film was 41% and 78% misplaced a 1" x 2" film product, with 50% placement concordance between the two films. Twenty-five women will have 80% power to determine whether there is a difference between polymer types of vaginal placebo films based on a McNemar's test evaluated at the .05 significance level. The sample size of 30 women will allow for additional input regarding challenges.

## **9.2 Statistical analyses**

McNemar's test will be used to assess differences in the proportion of misplaced films, defined as partial or unable to insert the vaginal film product based on visual assessment. McNemar's test will also be used to assess differences in preference for the two film products. Conditional logistic regression will be used to assess whether demographic characteristics such as age, race, and BMI are associated with product placement or product preference. Descriptive statistics will be used to summarize participants' challenges with self-insertion of the film products.

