### 4.3 Study Design Summary

After providing written informed consent, the participant will provide answers to a brief questionnaire, have urine collected for pregnancy testing, and have saliva collected for rapid HIV testing (unless a result from previous 6 months is available). Once deemed eligible, vaginal swabs will be collected (without a speculum) for sexually transmitted infection testing (gonorrhea, chlamydia and trichomonas).

The participant will then be randomized to insertion order for the two formulations of a placebo vaginal film [high and low ammonio-methacrylate copolymer type B (Eudragit®)]. Once a participant is randomized to the film, she is considered enrolled.

Clinic staff will obtain the films from the pharmacy and will provide instruction to the participant on the proper technique of self-insertion. The clinician and the participant will be in the same room during self-insertion of the films but will be separated by a privacy curtain. The clinician will be available to answer questions and document concerns/comments. The participant will attempt self-insertion of the first film and immediately afterward (within 10 minutes) the clinic staff will perform a speculum exam to determine the location of the film. The clinical staff will remove all visible film and ask the participant to complete a brief questionnaire regarding her experience with that specific film. The participant will then be asked to self-insert the second film. After the second film insertion, the clinical staff will perform another speculum exam to determine the film's location and remove any visible film. The participant will then answer another brief questionnaire regarding her experience with the second film as well as additional questions regarding her preference of film and questions surrounding challenges with self-insertion. It is anticipated that gonorrhea, chlamydia and trichomonas testing will be resulted within the week. Participants will be notified of any positive STI test reported by telephone, and necessary treatment and referrals will be provided. It should be noted that STI testing is provided in this study as a courtesy to the participants and not for eligibility purposes.

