### 6.2 Administration

After eligibility is confirmed, site staff will randomize the participant to sequence of film insertion. The site staff will retrieve two films from the pharmacy. The site staff will provide insertion instructions to the participant and the participant will self-insert the vaginal films in the order assigned by randomization. Neither the participant nor the study staff will know which film is the higher level or lower level film. The order of use will be documented in the participant's record.

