## **9.4 Random assignment**

The randomization scheme will be generated and maintained by a member of the Data Management Center at the study site and supplied to the Pharmacy. Women will be randomized to the sequence of insertion of the two films, low followed by high Eudragit® content or high followed by low Eudragit® content in a 1:1 ratio using a permuted block design with random block sizes of 2 and 4. In order to minimize bias in group assignment, participants will be given study identification numbers. A study staff member will allot the identification numbers in sequential order as participants become eligible to enroll in the study. Participants will be randomized using REDCap's randomization module to obtain the sequence of product insertion. The film product will be labeled in order to mask the Eudragit® content to the participants and study staff. The randomization scheme will be created for a total of 34 participants; the overage will be created to compensate for participant withdrawals or unusable products.

---

 UNAIDS Women and Girls and HIV. Accessed at

[https://www.unaids.org/sites/default/files/media\\_asset/women\\_girls\\_hiv\\_en.pdf](https://www.unaids.org/sites/default/files/media_asset/women_girls_hiv_en.pdf)

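### The primary McNemar test ignores the randomised insertion order; it is valid, but a sequence-based (Prescott) test would usually be slightly more powerful at almost no cost

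*Combined protocol and SAP*

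**What the plan says.** Section 9.2 (Statistical analyses) plans McNemar's "test will be used to assess differences in the proportion of misplaced films, defined as partial or unable to insert" the film. It also plans McNemar's test for preference, and a conditional logistic regression for which it names demographic characteristics only. Insertion order appears in neither.

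The design does control order. Section 9.4 randomises women to low-then-high or high-then-low "in a 1:1 ratio using a permuted block design with random block sizes of 2 and 4". Section 6.2 says "The order of use will be documented in the" participant's record. Section 4.3 puts both attempts in one visit: after the first examination, film removal and questionnaire, "The participant will then be asked to self-insert the second film".

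Section 9.1 bases power on an earlier cross-over study with 41% and 78% misplacement, "with 50% placement concordance between the two films". It concludes: "Twenty-five women will have 80% power to determine whether there is a difference between polymer types of vaginal placebo films", using a McNemar "test evaluated at the .05 significance level". The planned enrolment is 30.

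**The concern.** Self-insertion is a manual task done twice in a short time, so the second attempt may go better whichever film is used. A woman who fails only at her first attempt then becomes a discordant pair for a reason unrelated to Eudragit level. Pooled over balanced orders, these pairs cancel in McNemar's numerator but stay in its variance. The test would then reject too rarely under the null and lose some power against a real film difference. A test that compares the two randomised orders removes a practice effect common to both. What is at stake is efficiency. The validity of the test and the stated sample size are not in question.

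**Working it through.** **Inputs.** Section 9.1: misplacement 78% and 41%, concordance 50%, alpha 0.05 (sidedness not stated; two-sided assumed), 25 women for power, 30 planned. Section 9.4: 1:1 order in blocks of 2 and 4. Assumed: the practice effect, given as an odds ratio (OR) for improvement at the second attempt.

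**1. The plan's own figure.** Discordance is 1 − 0.50 = 0.50 and the difference is 0.78 − 0.41 = 0.37. The discordant cells are (0.50 + 0.37)/2 = 0.435 and (0.50 − 0.37)/2 = 0.065. Exact enumeration of the uncorrected McNemar test at N = 25 gives 80.2%, which reproduces the stated 80%. At N = 30 it gives 87.9%.

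**2. Validity under a practice effect.** Let a and b be the probabilities of misplacing only the first and only the second film, with no film effect. McNemar's numerator has mean (n1 − n2)(a − b), which is zero when the orders are balanced. Its true variance is N[(a + b) − (a − b)²], while the test assumes N(a + b). The ratio is 1 − (a − b)²/(a + b).

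With a + b = 0.50:
- a − b = 0.231: ratio 1 − 0.231²/0.50 = 0.89, type I error 3.6%.
- a − b = 0.381: ratio 1 − 0.381²/0.50 = 0.71, type I error 1.9%.
- No practice effect: type I error 4.75%.

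At 16:14, the worst split the blocks allow at N = 30, the two practice cases give 3.8% and 2.2%. Uncorrected McNemar would exceed 5% materially only at splits such as 20:10 (7% to 12%), which the blocking rules out.

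**3. Prescott's test.** For each woman, D = +1 if only the first film is misplaced, −1 if only the second, 0 otherwise. T is the sum of D in order 1. Over all women, S = ΣD and SS = ΣD². The permutation mean is n1·S/N and the variance is n1·n2/[N(N − 1)] × (SS − S²/N); z is compared with 1.96. A practice effect common to both orders cancels.

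**4. Power, N = 30, 15:15.** A random-intercept logit model was solved to 78%/41%/50% with no practice effect (base −0.428, film 1.901, SD 0.911). Then −ln(OR) was added at the second attempt and both orders were enumerated exactly.

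| Practice OR | McNemar (uncorrected) | Prescott (asymptotic) | Gain (points) |
|---|---|---|---|
| 1 | 87.9% | 88.4% | 0.5 |
| 1.65 | 88.3% | 89.2% | 0.9 |
| 2 | 87.8% | 89.2% | 1.4 |
| 3 | 85.7% | 88.6% | 2.9 |
| 4.5 | 81.6% | 86.9% | 5.3 |
| 7.4 | 73.7% | 83.5% | 9.8 |

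In this model average misplacement falls from 60% at the first attempt to 47% at the second at OR 2, 40% at OR 3 and 25% at OR 7.4.

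**5. Size, both films at 41% at the first attempt** (McNemar/Prescott): OR 1 4.4/4.7%; OR 2 3.9/4.8%; OR 3 3.3/4.9%; OR 7.4 2.2/4.8%. Over a wide null grid the maxima were 4.8% and 5.1%.

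**6. If the 41/78/50% figures already contain an order effect.** Refitting so that the averages over order match gives, at OR 1/2/3/5, McNemar 87.9/88.3/88.9/89.7% and Prescott 88.4/89.8/91.4/93.4%. Here McNemar loses nothing, though Prescott still gains.

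**7. Unequal orders.** With the two block sizes equally likely (assumed), 11% of lists end 16:14 in one direction or the other. At OR 3 McNemar has 88.2% if the harder film comes first in 16 women and 82.8% if it does so in 14; Prescott has 88.1% either way. At OR 2 in the favourable direction McNemar leads, 89.3% to 88.6%.

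**8. Other forms of the test.**
- Mid-p McNemar/Prescott: 87.9/87.3% at OR 1, 87.7/88.0% at OR 2, 85.5/87.2% at OR 3.
- Fully exact at OR 3: 79.2/81.6%. Both are below uncorrected McNemar (85.7%).
- Mainland-Gart, which drops concordant women: 84.9% at OR 3 and 79.1% at OR 4.5, both below McNemar, with size up to 5.7%.

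**The case against.** The plan contains no error. McNemar is valid, Sections 9.1 and 9.2 agree on it, its stated power reproduces, and small blocks already balance order. A preference for Prescott could be called taste.

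The practice effect has no size in the documents, and the larger gains need failure to fall by about half or more after one attempt. With no practice effect the like-for-like gain can be slightly negative (mid-p 87.9% against 87.3%; fully exact 82.3% against 81.6%). The historical figures come from a cross-over study and may already include an order effect, in which case McNemar's power does not drop at all. Much of the fall in the table is also beyond recovery, since Prescott itself goes from 88.4% to 83.5%.

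All of this stands as a limit on size. A second model, which fixes discordance at 50%, gives gains of 0.5 to 6.9 points at 15:15, and a 0.8-point lead for McNemar in one 16:14 case. So the magnitude depends on the model. None of it shows a material drawback of the asymptotic sequence-based test: at the most likely split it is no worse even without a practice effect, and its size stays within about 0.1 point of 5%.

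**Conclusion.** The point holds as a minor, optional improvement. The planned test is valid and the 80% claim is sound; with 25 women Prescott's test has 81.2% against McNemar's 80.2%, so changing the test does not disturb Section 9.1's power. At 15:15 the expected gain is 0.5 point with no practice effect and about 1.4 to 2.9 points at an odds ratio of 2 to 3. It reaches 5 to 10 points only under large assumed effects. In a minority of lists, in one direction, McNemar can lead by less than a point.

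The direction of the argument is firm. The figures rest on an assumed practice effect, the random-intercept logit model, a two-sided 0.05 level and 30 evaluable women. Neither test deals with a practice effect that depends on which film came first. No power claim is made for preference.

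**What to change.** In Section 9.2, prespecify for example:

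> The primary comparison is Prescott's test, two-sided 0.05, asymptotic form: the within-woman difference in misplacement (first minus second film: +1, 0, −1) is compared between the two randomised insertion orders. McNemar's test is supportive. Misplacement and preference are tabulated by film and insertion order.

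If a small-sample form is wanted, use the mid-p permutation version. Avoid the fully exact form, which is conservative, and Mainland-Gart, which discards the concordant women. For preference, the table by order is enough.

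The cost is a short addition to Section 9.2, a matching mention in Section 9.1 (where the power statement names McNemar) and a few lines of code, all fixed before unblinding. No data, visits or participants are added, because order is already recorded.

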#### **3.4 Secondary Endpoints**

- Percentage of participants who prefer the low level Eudragit® film to the high level Eudragit® formulation film with respect to insertion

- Participants' description of identified challenges

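### The McNemar test planned for film preference is in effect a sign test that ignores the randomised insertion order: valid, but less powerful if order sways preference

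*Combined protocol and SAP*

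**What the plan says.** Section 3.4 of the combined protocol and SAP defines the preference endpoint as "Percentage of participants who prefer the low level Eudragit® film to the high level Eudragit® formulation film with respect to insertion". Sections 4.3 and 5.2 place the preference questions after the second film, at the end of the single visit. For the analysis, section 9.2 states that McNemar's "test will also be used to assess differences in preference for the two film products". It adds a conditional logistic regression on demographic characteristics (age, race and BMI are the examples) for placement or preference. It mentions descriptive statistics only for insertion challenges.

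On order, section 9.4 says "Women will be randomized to the sequence of insertion of the two films", 1:1, and section 6.2 has the order of use documented for each participant. No analysis in section 9.2 uses sequence or period. Section 3.3 presents the preference objective as exploratory, and section 9.1 gives no power figure for it.

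**The concern.** McNemar's test compares two paired binary results per subject. Film placement gives such a pair, because each woman has a result for each film. An overall preference does not: it is one answer per woman. Put into a McNemar table, it becomes a test of whether the women who prefer low and those who prefer high are equally numerous, which is the sign test.

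That test pools the two sequences. The second attempt comes minutes after a first attempt and a speculum examination, and preference is judged with respect to insertion, so a pull towards the second film is plausible. If there is one, women in the two sequences have different chances of preferring low. The sign test uses a variance that ignores this and is too large. At stake is some power to detect a formulation preference, in a trial that already randomises and records the factor needed to recover it.

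**Working it through.** **The plan's own figure.** Section 9.1 states power only for the primary comparison: "Twenty-five women will have 80% power to determine whether there is a difference between polymer types of vaginal placebo films". Its inputs are misplacement of 41% and 78%, "with 50% placement concordance between the two films", and a "test evaluated at the .05 significance level" (sidedness not stated; two-sided assumed).

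- Discordance is 1 − 0.50 = 0.50 and the difference is 0.78 − 0.41 = 0.37. The discordant cells are (0.50 + 0.37)/2 = 0.435 and (0.50 − 0.37)/2 = 0.065.
- Connor form: n = [1.96·√0.50 + 0.8416·√(0.50 − 0.37²)]² / 0.37² = 26.18, so 27. The Miettinen form gives 24.07, so 25.
- Enumerated power at n = 25 is 80.2% for the uncorrected test.

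The stated figure reproduces, and nothing below affects it.

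**The two tests for preference.** Take 30 women (section 9.1), 15 per sequence (1:1 in section 9.4), all stating a preference. Let a be the number preferring low in the low-then-high sequence, and b the number preferring low in the high-then-low sequence.

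- Planned test (McNemar as a sign test): chi-square = [2(a + b) − 30]²/30 = 4(a + b − 15)²/30. With 30 answers it rejects at 21 or more, or 9 or fewer, preferring low.
- Stratified test: compare preferred position between sequences. The number preferring whichever film came first is k = a + (15 − b). The N-1 chi-square is 29(a + b − 15)²/[k(30 − k)].

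Both have the same numerator; only the variance differs. At k = 15 (no order effect in the data) the multipliers are nearly equal: 4/30 = 0.133 and 29/225 = 0.129. As k moves away from 15, the stratified multiplier grows. For example, a = 6 and b = 14 gives 20 of 30 preferring low. The exact sign test has p = 0.099. The stratified statistic has k = 7 and equals 29·25/(7·23) = 725/161 = 4.50, above the 5% critical value of 3.84.

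**Assumed model** (the documents give neither a preference rate nor an order effect). Logit P(prefers low) = logit(0.75) − s in low-then-high and logit(0.75) + s in high-then-low. Here s = logit(pull), and the pull is the share who would favour the second film if the formulations were equally liked. At a 75% pull, s = ln 3, so the chances of preferring low are 50% and 90%. At 85% they are 34.6% and 94.4%.

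**Exact enumeration over the two Binomial(15) counts, two-sided 0.05:**

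| Pull to second film | Average % preferring low | Power, planned | Power, stratified N-1 | Type I error, planned | Type I error, stratified |
|---|---|---|---|---|---|
| none (50%) | 75.0 | 80% | 80% | 4.3% | 4.3% |
| 65% | 73.3 | 74% | 76% | 3.4% | 4.0% |
| 75% | 70.0 | 59% | 67% | 1.9% | 4.2% |
| 85% | 64.5 | 29% | 52% | 0.5% | 3.9% |

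Type I error is computed with no formulation preference and the same pull. The mid-p form gives the same figures as N-1 here. Fisher's test in the stratified layout does not: its power is 67.5% with no order effect and 53.6% at a 75% pull, below the plan's 80% and 59%.

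**What an estimate would look like.** For example, 21/30 = 70%, exact 95% confidence interval 51% to 85%.

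**The case against.** The best defence is that nothing here is invalid. With sequences balanced, the sign test holds its type I error (at most 4.3% with 30 answers), and calling it McNemar's test is largely a matter of name. A reader might infer that the planned test is biased or wrong; it is not.

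Second, the gain depends on an order effect that the documents do not give. Up to a 65% pull it is under 2 points (74.2% vs 75.5%), and the 85% scenario is extreme. This stands.

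Third, a reader might take the fall from 80% to 59% as the price of the planned test. It is not. With strong order effects the average percentage preferring low, which is the section 3.4 endpoint, itself falls to 70%. With a true 70% and no order effect the sign test has 58.9% power anyway. Only the gap within a row, such as 59% vs 67%, belongs to the choice of test.

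Fourth, the version of McNemar's test is unstated, and the chi-square and exact forms can disagree when some answers are missing (20 v 9 gives p = 0.041 vs 0.061). With all 30 women stating a preference, both reject at 21 or more, so the contrast vanishes.

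Fifth, a reader might infer that women with no preference would be lost, or that the percentage would go unreported. The questionnaire is not shown, so whether such an answer is offered is unknown. An endpoint defined as a percentage implies that it will be reported. What is absent is its precision and a rule for such answers, which is missing detail rather than an error.

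**Conclusion.** The point holds as an efficiency point. The preference analysis reduces to a valid sign test that ignores the randomised order and turns conservative if order matters. Under the assumed model, stratifying by sequence costs no power when order has no effect. It adds 1 to 2 points at a 65% pull, about 8 at 75% and about 24 at 85%. These sizes rest on 15 women per sequence, a conditional 75% preference for low, additive log-odds, one overall preference per woman and a two-sided 0.05 level. None of the preference or order values comes from the documents. The endpoint is secondary and exploratory, and no sample-size claim depends on it, so priority is low.

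**What to change.** In section 9.2, replace the sentence on preference so that it:

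- tests formulation preference by comparing the preferred position (first or second) between the two randomised sequences, two-sided, with the N-1 chi-square or mid-p form or a logistic model with sequence, and not with Fisher's test, which has less power than the plan when order has little effect;
- reports the percentage preferring the low film among all women, overall and by sequence, with an exact 95% confidence interval;
- gives the exact binomial test as the unstratified check;
- shows any 'no preference' answers separately.

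The cost is wording only. Sequence is already documented under section 6.2 and preference is already collected under section 5.2, so no new data, visits or participants are needed.
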